 6. Time course of the response in eyes treated with GS010 IVT injection compared to eyes treated with sham IVT injection, for the BCVA reported with LogMAR, for parameters measured with HVF 30-2 and for parameters measured with SD-OCT, with comparisons from the RESCUE or REVERSE study baselines and pooled, to each follow-up study time point (2, 2.5, 3, 4, and 5 years) using mixed effects models with repeated measures (MMRM).
 7. Time course of the response in eyes treated with GS010 IVT injection compared to eyes treated with sham IVT injection, for contrast sensitivity measured with the Pelli-Robson chart with comparisons from the RESCUE or REVERSE study baselines and pooled, to follow-up study time points (2, 3, 4, and 5 years) using MMRM.
 8. Visual improvement as measured by LogMAR by analysis of covariance (ANCOVA) to determine the difference in improvement for all-GS010 eyes compared to all-sham eyes, for best-GS010 eyes compared to best-sham eyes and for worst-GS010 eyes compared to worst-sham eyes, with comparisons from the RESCUE or REVERSE study baselines and pooled, to each follow-up study time point (2, 2.5, 3, 4, and 5 years).
 9. Change of ganglion cell layer (GCL) thickness/volume and topographical map and other parameters measured by SD-OCT (e.g., retinal nerve fiber layer and quadrantal thickness analyses) for all-GS010 eyes compared to all-sham eyes, for best-GS010 eyes compared to best-sham eyes and for worst-GS010 eyes compared to worst-sham eyes, from the RESCUE or REVERSE study baselines and pooled, to each follow-up study time point (2, 2.5, 3, 4, and 5 years) using (MMRM).

10. QOL as measured with the Visual Functioning Questionnaire 25 (VFQ-25) and 36-Item Short Form Health Survey, version 2 (SF-36-v2) subject-rated instruments and summarized descriptively with within-group comparisons from the RESCUE or REVERSE study baselines and pooled, to each follow-up study time point (2, 2.5, 3, 4, and 5 years).

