11.5.2.2 LogMAR

Analysis for European Medicines Agency

The primary analysis will be performed on the intent-to-treat (ITT) population. The change from baseline to each follow-up visit in the LogMAR acuity will be the response. The change from baseline of all-GS010 eyes will be compared to the change from baseline of all-sham eyes (intra-subject comparison) using a mixed-effects ANCOVA model using the following terms (or covariate) in the model:

- Subject and eyes of the subject as random factors
- The baseline LogMAR
- Treatment

The investigative site will not be included in this analysis as the number of subjects recruited per site will be very small. However, stratification by geographical area will be performed as a sensitivity analysis. Neighboring countries can be pooled to reach at least 9 subjects per geographical entity. The analysis will be performed based on alpha of 0.05 (two-sided test).

An additional model will add the treatment by geographical interaction to investigate lack of generalizability of the treatment effect.

Analysis for Food and Drug Administration

The primary analysis will be performed on the ITT population. The change from baseline of the best-GS010 treated eyes will be compared to the change from baseline of the best-sham eyes (inter-subject comparison) using an ANCOVA with baseline LogMAR as covariate. The analysis will be performed using an alpha of 0.05 (two-sided test). The statistical significance in favor of the best-GS010 treated eyes against the best-sham eyes will show evidence of the advantage of using GS010 for halting visual acuity loss or improving visual acuity in subjects with LHON. The difference in the mean change from baseline (adjusted mean difference) between the two treatment groups and associated 95% confidence interval will be reported.

The center will not be included in the analysis as the number of subjects recruited per site will be very small. However, stratification by geographical area will be performed as a sensitivity analysis. Neighboring countries can be pooled together to reach at least 9 subjects per geographical entity. The pooling of countries will be performed during the masked review of data.

An additional model will add the treatment by geographical area interaction to test for a lack of generalizability of the treatment effect.

The same analysis will be repeated for worst-GS010 treated eyes against worst-sham eyes.

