8.5 EFFICACY ANALYSES

All efficacy analysis will be conducted on the mITT Population, the PP Population, and additionally in subset populations as appropriate. All summaries will be performed on RESCUE separately, REVERSE separately, and on RESCUE and REVERSE combined.

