- The change of LogMAR BCVA from nadir to the visit of interest

Analysis for European Medicines Agency (EMA)

The primary analysis will be performed on the mITT Population. The change from baseline to each follow-up visit in the LogMAR acuity will be the response. The change from baseline of all-GS010 eyes will be compared to the change from baseline of all-sham eyes applying a mixed-effects ANCOVA model using the following terms (or covariate) in the model:

- Subject as a random factor.
- The baseline LogMAR as a covariate.
- Treatment as a fixed effect.

The null and alternative hypotheses for the EMA LogMAR analysis are:

$$H_0: \mu_{\text{All-GS010}} = \mu_{\text{All-Sham}}$$

$$H_1: \mu_{\text{All-GS010}} \neq \mu_{\text{All-Sham}},$$

where μ presents the mean change from baseline to the visit of interest in LogMAR and “All” represents all eyes treated with GS010 or Sham.

The investigative site will not be included in the analysis as the number of subjects recruited per site will be very small. However, stratification by geographical area may be performed as a sensitivity analysis. Neighboring countries can be pooled to reach at least 9 subjects per geographical entity. The analysis will be performed using an alpha of 0.05 (two-sided test).

An additional model may add the treatment by geographical interaction (geographical areas: USA and Europe) to investigate the generalizability of the treatment effect. The following model diagnostics may be checked: normality of error terms, independence of error terms, independence of the covariate and treatment effect, and homogeneity of error variances.

Analysis for Food and Drug Administration

The primary analysis will be based on the mITT Population. The change from baseline of the best-GS010 treated eyes will be compared to the change from baseline of the best-sham eyes (inter-subject comparison) using an ANCOVA with baseline LogMAR as covariate. The analysis will be performed using an alpha of 0.05 (two-sided test). The statistical significance in favor of the best-GS010 treated eyes against the best-sham eyes will show evidence of the advantage of using GS010 for halting visual acuity loss or improving visual acuity in subjects with LHON. The difference in the mean change from baseline (adjusted mean difference) between the two treatment groups and associated 95% confidence interval will be reported.

The null and alternative hypotheses for the FDA LogMAR analysis are:

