8.5.2.4 Responder Analysis

Eye Level – Eye Responder

LogMAR BCVA

Eye Responder analyses will be carried out at the visit of interest for the following definitions:

- Eyes with an improvement of at least 15 ETDRS letters (equivalent to a decrease of at least 0.3 LogMAR) compared to baseline, or having a Snellen acuity equivalent better than 20/200.
- Eyes that lost less than 15 ETDRS letters (equivalent to an increase of less than 0.3 LogMAR) compared to baseline.
- For eyes with on-chart BCVA at baseline, an improvement of at least 15 ETDRS letters (equivalent to a decrease of at least 0.3 LogMAR) compared to baseline.

Number and percentage of responders and non-responders will be summarized at all the follow-up visits (Years 2, 2.5, 3, 4 and 5). A GEE model will be used for comparisons of all-GS010 eyes against all-sham eyes to each of the follow-up visits.

The analysis will also be performed to compare best-GS010 eyes against best-Sham eyes and worst-GS010 eyes against worst-Sham eyes, giving number and percentage of responders and non-responders. However, instead of using a GEE model, a logistic regression will be used for these analyses, as the data are independent.

The following responders analyses will be performed on all eyes, all GS010 eyes and all sham eyes.

- Eyes with Clinically Relevant Recovery (CRR) from baseline at visit of interest, defined as:
 - For eyes on-chart at baseline, an improvement of at least -0.2 LogMAR from baseline at visit of interest,
 - For eyes off-chart at baseline, eyes which became on-chart ($\text{LogMAR} \leq 1.6$) at visit of interest.
- Eyes with Clinically Relevant Recovery (CRR) from Nadir at visit of interest, defined as:
 - For eyes on-chart at Nadir, an improvement of at least -0.2 LogMAR from Nadir at visit of interest,
 - For eyes off-chart at Nadir, eyes which became on-chart ($\text{LogMAR} \leq 1.6$) at visit of interest.
- Eyes with change from baseline of at least -0.3 LogMAR at visit of interest
- Eyes with change from nadir of at least -0.3 LogMAR at visit of interest
- Eyes with change from baseline of at least -0.2 LogMAR at visit of interest
- Eyes with change from nadir of at least -0.2 LogMAR at visit of interest
- Eyes with $\text{BCVA} < 1$ LogMAR at visit of interest
- Eyes with $\text{BCVA} \leq 1$ LogMAR at visit of interest
- Switch from baseline off-chart to on-chart ($\text{LogMAR} \leq 1.6$) at visit of interest
- Number/percentage of on-chart eyes at visit of interest

LogCS

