8.7 EXPLORATORY ANALYSES

8.7.1 Exploratory efficacy analyses

As an exploratory analysis, the response to treatment through Visit 5 (Year 5) using a MMRM model will be performed. The change from baseline in the LogMAR will be the response. Change from baseline of all-GS010 eyes will be compared to the change from baseline of all-sham eyes. The model will include subject as a random factor and fixed effects for treatment, follow-up visit (time point), eye status at baseline (better or worse), time from onset of disease and LogMAR at baseline as a covariate. The following interactions will be explored: baseline LogMAR and treatment; time from onset of disease and treatment; and eye status at baseline and treatment. The estimate of treatment effect at various follow-up time points and its 95% confidence interval (CI) will be presented. A UN@AR(1) (Autoregressive(1)) covariance structure will be fit to accommodate the doubly repeated measures data (repeated over time and eye). In the event of convergence problems with this covariance structure, other covariance structures will be explored.

Time course analysis of log of contrast sensitivity (LogCS), Humphrey visual field parameters and SD-OCT parameters will be conducted similarly to the time course analysis of LogMAR.

Other exploratory analyses will be performed for all analysed visits as a sensitivity analysis, excluding off-chart evaluations whose distance to the subject was superior to 2 meters. The endpoints analysed will be the ones described in 8.5.2.2 at eye level.

Additional exploratory analyses may be performed in the study.

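### The pooled best-eye and worst-eye models leave out the source trial (RESCUE or REVERSE), which costs precision but does not by itself bias the estimate

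*SAP*

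**What the plan says.** **Pooling.** SAP 8.5 states: "All summaries will be performed on RESCUE separately, REVERSE separately, and on RESCUE and REVERSE combined". Protocol 7.2.2, secondary endpoint 8, plans the LogMAR ANCOVA for all, best and worst eyes, "with comparisons from the RESCUE or REVERSE study baselines and pooled, to each follow-up study time point".

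**Best-eye ANCOVA.** In the FDA part of SAP 8.5.2.2, the change in best-GS010 eyes "will be compared to the change from baseline of the best-sham eyes (inter-subject comparison) using an ANCOVA with baseline LogMAR as covariate". Baseline LogMAR is the only covariate named. Protocol 11.5.2.2 gives the same model.

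**Worst-eye ANCOVA.** Protocol 11.5.2.2 adds: "The same analysis will be repeated for worst-GS010 treated eyes against worst-sham eyes". SAP 8.5.2.2 names only worst-eye summaries, but the opening of SAP 8 says that ANCOVA will be run on all continuous endpoints.

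**Best-eye and worst-eye responders.** SAP 8.5.2.4 says that "instead of using a GEE model, a logistic regression will be used for these analyses, as the data are independent". It gives no list of terms; SAP 8.8 says only that the new models allow control for baseline.

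**Elsewhere.** Source trial is absent from the predetermined covariates (SAP 4.4), the EMA model (8.5.2.2), the SD-OCT model (8.5.2.3), the exploratory MMRM (8.7.1) and the list of changes (8.8). The only stratification mentioned is by geographical area, as an optional sensitivity analysis.

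**The concern.** In the all-eyes comparison every subject contributes one eye to each arm, so a difference in level between the trials falls equally on both arms. In the best-eye comparison each subject contributes one eye to one arm. Once the trials are pooled, RESCUE eyes are compared in part with REVERSE eyes, and a difference in mean change between the trials does not cancel within subject. If it is not modelled, it goes into the error term.

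No other term reliably stands in for the trial. SAP 4.4 names duration of vision loss as possibly prognostic and says that its covariates will be used in the efficacy analyses, but the FDA model lists baseline LogMAR alone.

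The SAP treats a significant best-eye result as evidence of benefit. The sample is fixed by the parent trials, so lost precision cannot be recovered by recruitment. Nor does any pooled model estimate whether the effect differs by trial. SAP 8.8 drops the treatment-by-geography model, although 8.5.2.2 still lists it as optional.

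**Working it through.** **Inputs from the documents.** Alpha 0.05 two-sided (SAP 8.5.2.2). Allocation 1:1 by right eye, with Efron's method used to balance treatment over best-seeing and worst-seeing eyes (SAP 3.1). One ETDRS letter is 0.02 LogMAR (Protocol 9.6.5). There is no sample size, SD or effect figure to reproduce; SAP 3.3 says that no formal calculation was made.

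**Inputs assumed.** D, the difference between the trials in mean LogMAR change that remains after adjustment for baseline LogMAR: 0 to 0.4. Residual SD s: 0.4 or 0.6. Two trials of equal size.

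**Step 1: error variance.** With two equal trials, an omitted study effect adds D²/4 to the residual variance. The inflation is (s² + D²/4)/s², and the equivalent loss of subjects is 1 − 1/inflation.

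| D | s = 0.4: inflation (loss) | s = 0.6: inflation (loss) |
|---|---|---|
| 0 | 1.00 (0%) | 1.00 (0%) |
| 0.2 | (0.16 + 0.01)/0.16 = 1.06 (6%) | (0.36 + 0.01)/0.36 = 1.03 (3%) |
| 0.3 | (0.16 + 0.0225)/0.16 = 1.14 (12%) | (0.36 + 0.0225)/0.36 = 1.06 (6%) |
| 0.4 | (0.16 + 0.04)/0.16 = 1.25 (20%) | (0.36 + 0.04)/0.36 = 1.11 (10%) |

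**Step 2: simulation.** 3,000 runs per setting compared ANCOVA on treatment and baseline with and without a study term. Efron's biased coin (2/3) was run within each trial and the true effect was 0.3 LogMAR. Results for an assumed 30 subjects per trial (without / with the study term):

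| s | D | Mean model SE | Power | Type I error |
|---|---|---|---|---|
| 0.4 | 0 | 0.104 / 0.104 | 0.81 / 0.81 | 0.041 / 0.041 |
| 0.4 | 0.2 | 0.107 / 0.104 | 0.79 / 0.80 | 0.046 / 0.053 |
| 0.4 | 0.4 | 0.117 / 0.104 | 0.73 / 0.81 | 0.032 / 0.047 |
| 0.6 | 0 | 0.156 / 0.156 | 0.48 / 0.47 | 0.048 / 0.049 |
| 0.6 | 0.4 | 0.164 / 0.155 | 0.43 / 0.47 | 0.044 / 0.052 |

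The SE ratio at s = 0.4, D = 0.4 is 0.117/0.104 = 1.125, against √1.25 = 1.118 from Step 1. In the same setting, power goes from 0.53 to 0.62 with 20 subjects per trial and from 0.84 to 0.90 with 38. Mean bias was within 0.004 LogMAR of zero in every setting, with or without the term.

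**Step 3: unequal trial mix.** If the share of one trial differs between best-GS010 and best-sham eyes, the unadjusted estimate moves by D × (difference in shares). A 10-point difference at D = 0.2 to 0.4 gives 0.02 to 0.04 LogMAR, or 1 to 2 letters. Splits of 17:13 in one trial and 13:17 in the other give 17/30 − 13/30 = 0.133, hence 0.027 LogMAR at D = 0.2 and 0.053 at D = 0.4. These mixes are illustrations; the documents report none.

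**Step 4: precision of a study-by-treatment estimate.** With equal trials, each within-trial effect has twice the variance of the pooled effect, so their difference has four times the variance and twice the SE. At 30 per trial and s = 0.4 that is 2 × 0.104 = 0.208, a 95% half-width of about 1.96 × 0.208 = 0.41 LogMAR. It can describe consistency but not test it with useful power.

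**The case against.** **By-trial results are already planned.** SAP 6.4 makes each trial an analysis subset, and SAP 8.5 puts the separate results beside the combined one. This stands and lowers the stakes. What is missing is a pooled estimate that respects the trials, and an interval for the difference between them.

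**Randomisation protects the comparison.** A reader might infer that the pooled estimate is systematically biased. The documents do not support that. Treatment was balanced over best and worst eyes, and the on-chart and paediatric subsets are defined by pre-treatment characteristics. A chance imbalance in mix is part of sampling error, not a second harm. The per-protocol set (SAP 6.3) is different, because it depends on completing follow-up, but nothing in the documents shows that completion shifts the trial mix between arms. The documents also do not say outright that Efron's method was run separately in each trial; the simulation assumes that it was.

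**The all-eyes models are not the problem.** This stands. The EMA ANCOVA, the all-eyes GEE and the exploratory MMRM compare the two eyes of the same subjects, and the MMRM also includes time from disease onset.

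**The logistic models are unspecified.** SAP 8.5.2.4 is silent on terms, so it does not exclude study. That is a reason to state the term. The variance formula in Step 1 does not carry over to logistic regression.

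**Motive.** It is tempting to read the separate analyses as an admission that the trials differ. Neither document gives that reason.

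**Conclusion.** The point holds for the pooled best-eye and worst-eye ANCOVA and logistic models: none of them names the trial in which the subject was randomised. The expected consequence is lost precision and a conservative test, not a false-positive claim. For D from 0 to 0.4 LogMAR after baseline adjustment and two equal trials, ANCOVA error variance is inflated by 0-25% at residual SD 0.4 and by 0-11% at SD 0.6. If D is zero, nothing is lost. Every one of these figures rests on assumed inputs; the omission itself is read directly from the text.

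A shift in the estimate needs a trial mix that differs between arms, by chance or through post-treatment selection such as the per-protocol set. All efficacy analyses here are secondary (SAP 8.5.4) and the primary endpoint is descriptive safety, so this is an improvement worth making rather than a flaw that undermines the study.

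**What to change.** Add study (RESCUE/REVERSE) as a fixed effect in the pooled best-eye and worst-eye ANCOVA and logistic models, and list the logistic terms explicitly in SAP 8.5.2.4. For the same comparisons, report one study-by-treatment estimate with its 95% CI beside the by-trial results, labelled as a descriptive consistency check. The all-eyes within-subject models do not need the study main effect.

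The main effect costs one degree of freedom and needs no new data. In the logistic models the odds ratio becomes conditional on study, which should be stated. The SAP should also say how the estimated proportions promised in SAP 8 are averaged over the two trials.

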4.4 PREDETERMINED COVARIATES AND PROGNOSTIC FACTORS

GCL thickness/volume and topographical maps, best or worst-seeing eye (eye status) as determined prior to randomization and duration of vision loss at the time of treatment could be significant prognostic factors for the treatment effect.

The baseline LogMAR will also be used as a covariate for analysis of change in LogMAR. Similarly, the baseline of the endpoint being analyzed will be used as the model's covariate.

The investigative site will not be included in the analysis as the number of subjects recruited per site will be very small. However, stratification by geographical area may be performed as a sensitivity analysis. Neighboring countries can be pooled to reach at least 9 subjects per geographical entity. All analysis will be performed using an alpha of 0.05 (two-sided test).

These covariates will be used in the analyses presented in [Section 9.5 Efficacy Analysis](#).

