5.5 HANDLING OF MISSING DATA AND/OR INVALID DATA AND OUTLIERS

5.5.1 Efficacy

In case of missing data, the following rules will be applied as a primary imputation method applicable to all visits of interest (follow-up study time points 2, 2.5, 3, 4 and 5 years):

For all analysis timepoints, a review of the visits with available BCVA value will be done by GenSight to decide, for each patient, which visit will be used for this specific timepoint analysis. The document will be provided in excel format, and then imported in SAS in order for the statistician to perform the analysis (CLIN-06_DRM_Listings_V1.0_30JUN2022).

If Year-2 visit is not available at Clin06 inclusion, then “Follow-up Visit 12” (corresponding to Week 96) from Clin03A/Clin03B will be used.

After this affectation, in case of missing LogMAR value at a visit, LOCF will be applied with all analysed visits.

When a test result score/value for the Pelli-Robson Contrast test is missing at any visit for the reason that the subject was unable to perform because the vision was too poor, the following convention will be used: the worst possible score for the given test will be assigned as the value for that visit (i.e., 0 LogCS).

The imputation method of missing data used in each analysis will be specified in the TFLs in a footnote.

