$$H_0: \mu_{\text{Best-GS010}} = \mu_{\text{Best-Sham}}$$

$$H_1: \mu_{\text{Best-GS010}} \neq \mu_{\text{Best-Sham}},$$

where μ presents the mean change from baseline to the visit of interest in LogMAR and “Best” represents the best-seeing eyes.

The following model diagnostics may be checked: linearity of regression, normality of error terms, independence of error terms, independence of the covariate and treatment effect, homogeneity of error variances, homogeneity of regression slopes.

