8.5.4 Multiplicity

The primary objective of this study is to assess the long-term safety of intravitreal GS010 administration up to 5 years post-treatment in subjects who were treated in the RESCUE or REVERSE studies. All efficacy analysis will be secondary analysis. No adjustment of multiplicity will be applied.

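### The plan says significance in favour of best-GS010 eyes will show an advantage, but names no visit or data set to carry that conclusion and leaves all efficacy tests unadjusted

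*SAP*

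**What the plan says.** Under the FDA heading of SAP 8.5.2.2, change from baseline in LogMAR is compared between best-GS010 and best-sham eyes. The method is a between-subject ANCOVA with baseline LogMAR as covariate, in the mITT population, at two-sided 0.05. The section then says what a significant result will mean: "The statistical significance in favor of the best-GS010 treated eyes against the best-sham eyes will show evidence of the advantage of using GS010", with reference to halting or improving visual loss. Protocol 11.5.2.2 has the same sentence, there for the ITT population.

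The hypothesis is not fixed in time. The mean in H0 "presents the mean change from baseline to the visit of interest in LogMAR and “Best” represents the best-seeing eyes". SAP 5.5.1 lists five such visits when it calls its imputation rules "applicable to all visits of interest (follow-up study time points 2, 2.5, 3, 4 and 5 years".

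It is not fixed to a data set either. SAP 8.5 says: "All summaries will be performed on RESCUE separately, REVERSE separately, and on RESCUE and REVERSE combined". That sentence speaks of summaries, but the ANCOVA endpoint itself (Protocol 7.2.2, endpoint 8) is defined "with comparisons from the RESCUE or REVERSE study baselines and pooled, to each follow-up study time point (2, 2.5, 3, 4, and 5 years".

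SAP 4.4 applies the same alpha to every analysis. SAP 8.5.4 classes all efficacy as secondary and adds: "No adjustment of multiplicity will be applied".

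**The concern.** Unadjusted secondary p-values are acceptable when they are offered as description. Here one sentence goes further and attaches a conclusion about the product to statistical significance. That conclusion has its usual 2.5% risk of a false result in favour only if it rests on one test fixed in advance.

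As written, a favourable p-value at any visit, in either trial or in the pooled data, satisfies the sentence even if pooled Year 5 shows nothing. The Year 2 visit could do so too. It is ideally combined with the parent trials' Week 96 visit, and SAP 5.5.1 substitutes the Week 96 value where no Year 2 visit is available. A study meant to examine durability could then state an advantage on a parent-trial time point.

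**Working it through.** **Inputs from the documents.** Alpha is 0.05 two-sided (SAP 8.5.2.2), so 0.025 in the direction favouring GS010. There are five visits (SAP 5.5.1) and three data sets (SAP 8.5; Protocol 7.2.2, endpoint 8). The contrast and population are best-GS010 versus best-sham in mITT. There is no adjustment (SAP 8.5.4). The number of tests that can trigger the sentence is 5 × 3 = 15.

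**The plan's own figure.** For one test, P(|z| > 1.96) = 0.050 and P(z > 1.96) = 0.025. The stated alpha is reproduced for a single named test. The plan gives no sample size, power or family-wise figure to check.

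**Assumptions.** The correlation ρ between visits of the test statistics is not in the documents, so a range is shown. Each trial contributes five standard normal statistics with common correlation ρ. RESCUE and REVERSE are independent and equally weighted, so the pooled statistic at each visit is z_P = (z_A + z_B)/√2. There is no true effect.

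**Quantity computed.** P(at least one of the 15 statistics > 1.96), by simulation with 400,000 draws per setting. The pooled-only column uses the five-visit result for a single data set, because z_P has the same between-visit correlation as z_A.

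| ρ (assumed) | 15 tests, in favour | ÷ 0.025 | Pooled only, 5 visits, in favour | ÷ 0.025 |
|---|---|---|---|---|
| 0.5 | 0.197 | 7.9 | 0.092 | 3.7 |
| 0.7 | 0.160 | 6.4 | 0.074 | 3.0 |
| 0.8 | 0.139 | 5.6 | 0.064 | 2.5 |
| 0.9 | 0.113 | 4.5 | 0.052 | 2.1 |
| 0.95 | 0.096 | 3.8 | 0.043 | 1.7 |
| 0.99 | 0.074 | 3.0 | 0.033 | 1.3 |

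**Sensitivity.**
- Correlation decaying with time, at 0.7 / 0.8 / 0.9 / 0.95 per year, gives 0.169 / 0.148 / 0.119 / 0.100 over the 15 tests.
- Weighting the trials 40:60 at ρ = 0.8 gives 0.139, essentially unchanged.
- One visit in three data sets gives about 0.058, or 2.3 times 0.025.

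**What naming one test removes.** If pooled Year 5 is the named test, its own risk is 0.025. The remaining chance, that some other best-eye test favours GS010 while pooled Year 5 does not, is the 15-test figure minus 0.025. At ρ = 0.7 this is 0.160 − 0.025 = 0.135; at ρ = 0.95 it is 0.096 − 0.025 = 0.071.

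**The case against.** The strongest reply is that the study's primary objective is safety. SAP 8.5.1 says there is no primary efficacy variable, no sample size was calculated, and SAP 8.5.4 openly declares all efficacy secondary and unadjusted. On that view nothing is hidden and the problem is one sentence of wording. Much of this stands. Multiplicity was not overlooked, and an unadjusted descriptive analysis would need no change. But 8.5.4 does not say that p-values are nominal or that no claim will rest on them, so it does not neutralise the sentence in 8.5.2.2. The two sections pull in different directions.

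The size is also open to challenge. The multiples are against 0.025; against the stated two-sided 0.05, a risk of 0.16 to 0.10 is only about 3 to 2 times. LOCF (SAP 5.5.1) pushes the between-visit correlation up, towards the smaller figures. Both points stand.

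A reader might infer more than the documents support:
- *That no test is specified, or that the population is open.* Method, covariate, contrast, alpha, hypotheses and mITT are all named, and SAP 6.3 makes Per Protocol supportive. Only visit and data set are missing.
- *That Per Protocol, subset or EMA all-eyes tests belong in the count, giving 30 tests or more.* The FDA paragraph bases its primary analysis on mITT, and the EMA paragraph has hypotheses and an alpha but no sentence saying what significance will show. The count for this sentence is 15.

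**Conclusion.** The point holds as a conflict between confirmatory wording in SAP 8.5.2.2 and Protocol 11.5.2.2 and the unadjusted, secondary status given in SAP 8.5.4, with visit and data set left unnamed. If any of the 15 mITT best-eye results may carry the conclusion, the false in-favour risk is about 0.16 to 0.10 at assumed ρ of 0.7 to 0.95 (0.20 to 0.07 over 0.5 to 0.99), against 0.025. If only the pooled data count, it is about 0.074 to 0.043 at ρ of 0.7 to 0.95.

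It is tempting to state a fixed inflation of four to six times. The documents do not support that as a fact: it needs ρ of roughly 0.75 to 0.94 and needs every visit and data set to count as a claim. That efficacy is a secondary objective limits the weight of the point but does not remove it.

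**What to change.** Change SAP 8.5.2.2 and Protocol 11.5.2.2 together; editing the SAP alone leaves the sentence in the Protocol. Two routes resolve the conflict.

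1. Tie the sentence to one test: the ANCOVA of best-GS010 versus best-sham eyes at Year 5, pooled RESCUE and REVERSE, in the mITT population, with the Protocol's ITT label aligned. State that all other efficacy p-values are nominal and no basis for a claim. The SAP is dated 30 June 2022, and interim analyses were planned after the Year 3 and Year 4 visits. The documents do not say whether these had been run, so the SAP should disclose whether their results were known when the test was named. No adjustment of the remaining tests is needed.
2. Delete the sentence and report all efficacy contrasts descriptively with unadjusted 95% confidence intervals, in line with SAP 8.5.4. This is the cleaner route if interim results were already known.

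Either route costs wording only, with no new data or analyses. The sponsor gives up the option of presenting an isolated significant result at an earlier visit, or in one trial, as evidence of advantage. Under the second route, no efficacy p-value carries that conclusion.
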